1.0 OBJECTIVES

1.1 To determine the efficacy of intravenous busulfan, dose targeted to achieve AUC of 700-900 combined with fractionated total body irradiation and VP16 as a preparative regimen for marrow transplantation from an HLA-identical sibling in patients with advanced hematological malignancies (AML or ALL) beyond 2nd remission, induction failure, in relapse, chronic myelogenous leukemia in blast crisis and myelodysplasia (RAEB and RAEBIT).

Rev. 6/13/02 1.2 To determine the efficacy of this regimen in patients with AML in first remission with unfavorable cytogenetics.

1.3 To evaluate the early and late toxicities of this regimen.

2.0 BACKGROUND AND HYPOTHESIS

During the last 20 years clinical bone marrow transplantation from a histocompatible sibling donor has evolved into an important treatment modality for patients with acute lymphoblastic leukemia, acute myelogenous leukemia and chronic myelogenous leukemia. If the transplant procedure is performed in first complete remission of acute leukemia or during chronic phase or chronic myelogenous leukemia, approximately 50-70% of patients become disease free long-term survivors.⁽¹⁻⁸⁾ In contrast, the chances for an ultimately successful outcome of bone marrow transplantation drops to 10-40% if this is performed during second or subsequent complete remission, during relapse of acute leukemias, or while patients with chronic myelogenous leukemia are in accelerated or blast phase of this disease. In the latter group of patients the probability of leukemic relapse is in the range of 40-70%.⁽⁹⁻¹⁶⁾ Many transplant centers have performed several phase I-II trials of preparative regimens using alternative chemotherapeutic agents or methods of administering TBI. Some of these studies suggest a decrease in the post-transplant relapse rate that are often associated with increased transplant related morbidity and mortality from regimen related toxicity.⁽¹⁷⁻²⁰⁾ At the City of Hope a phase I/II trial was conducted in 1986 to determine the efficacy of substituting etoposide (VP-16) for cyclophosphamide in combination with fractionated total body irradiation (FTBI). This trial was done in 33 patients with acute leukemia beyond first remission, and resulted in a 43% long-term disease free survivorship. Despite this improved survival compared to previous studies there still is significant relapse rate, particularly in patients with advanced leukemia. This regimen has subsequently been utilized to treat 100 patients with acute leukemia in remission. There was only one case of fatal veno-occlusive disease; otherwise the regimen was well tolerated.⁽²¹⁾ Studies combining busulfan and cyclophosphamide as a preparative regimen for patients with advanced hematological malignancies have been reported to result in similar or superior outcomes when compared with standard cyclophosphamide and TBI regimens, suggesting that busulfan has important anti-leukemic effects. A randomized Southwest Oncology Group study (SWOG) comparing busulfan, cyclophosphamide with FTBI VP-16 showed 20% disease free survival for patients transplanted with advanced leukemia.⁽²²⁾ At City of Hope a phase I study was conducted utilizing escalating doses busulfan in combination with fixed doses of

FTBI and VP-16 in an attempt to decrease the relapse rate in those patients transplanted for advanced hematological malignancies. The rationale behind the study was that we combined three non-cross resistant anti-leukemic agents with non-overlapping extramedullary toxicities. An in vitro synergy has been demonstrated between busulfan/VP-16 and busulfan/VP-16 has been proven to be an effective regimen for relapsed leukemia and for ABMT for AML in first and second remission.^{23,24} The dose limiting toxicity occurred at 12mg/kg the MTD was defined at 11mg/kg. At this dose level median first dose AUC for these patients was 892 μ M*min (460-1267). With a median follow-up of 11.5 months, the disease-free survival is 32%, and the probability of relapse is 40%. The only variable predictive of a disease-free survival and relapse was the busulfan dose of 7-8 mg/kg. In this phase I study there was a wide variability of the AUC of busulfan due to the variability of absorption of oral busulfan. An AUC of 700-950 showed a trend to a decreased relapse rate and improved disease free survival.

A phase II study utilizing IV busulfan was conducted at City of Hope which has resulted in FDA approval of IV busulfan and it is proposed to substitute IV busulfan which has been shown to have more predictable pharmacokinetic properties than the oral preparation resulting in a better toxicity profile.^(25,26,27)

Rev. 6/13/02

*Patients with AML in first complete remission (CR1) with unfavorable cytogenetics have a relapse rate of 40% with our current transplant regimen consisting of fractionated radiation and etoposide. We propose to use this new preparative regimen to see if it can improve the DFS and relapse rate for this subset of patients with AML in first CR.

3.0 DRUG INFORMATION

3.1 Busulfan (Myleran)

3.11 Mechanism of Action: Busulfan is a bifunctional alkylating agent. In aqueous media, busulfan hydrolyses to produce reactive carbonium ions that can alkylate DNA.

3.12 Formulation and stability: Busulfan injection is a sterile, pyrogen-free solution provided in a mixture of dimethylacetamide (DMA) and polyethlyeneglycol 400 (PEG 400). It is supplied in 10-ml single use ampules at a concentration of 6-mg Busulfan per ml. Each ampule contains 60mg of Busulfan in 3.3 ml of DMA and 6.7 ml of PEG 400. When diluted in normal saline or D5W to a concentration of 0.5mg/mL, the resulting solution must be administered within eight (8) hours of preparation; including the 2 hours of infusion of the drug.

Stable at 4° C for at least twelve months. Ampules should be stored refrigerated at 2-8° C. Do not freeze. Ampules may be stored for up to seven days at room temperature.

Solution preparation: prepare the Busulfan solution as follows: Use sterile, non-pyrogenic, disposable containers, syringes, needles, stopcocks, and transfer tubing, etc. Calculate the amount of drug to be administrated based on the dosage and the patient's body weight.

Prepare a solution of 0.9% sodium chloride injection USP (normal saline) calculated Busulfan dose in ml from the step above.

Break off the top of the ampule and remove the calculated volume of Busulfan from the container by using a syringe fitted with a filter needle or equivalent. Transfer the contents of the syringe into the calculated amount of either normal saline or D5W making sure that the drug flows into and through the solution. Mix by inverting the bag.

3.13 Administration: Each dose of the drug will be given by slow central intravenous infusion over 2 hours. Caution: Do not administer as an intravenous push or bolus.

3.14 Supplier: This drug is commercially available; manufactured by Orphan Medical Inc.

3.15 Toxicity: Toxicity from busulfan includes:

- a). Severe bone marrow hypoplasia, which would be fatal without administration of bone marrow, stem cells.
- b). Nausea and vomiting which can be decreased by the use of sedation and anti-emetics.
- c). Stomatitis and diarrhea which can be treated symptomatically with fluid replacement and atropine or diphenoxylate H C1.
- d). Pulmonary fibrosis characterized by delayed onset of cough, shortness of breath and low-grade fever.
- e). Hepatic damage, which can occur in combination with cytoxan or as a single agent and can result in significant hepatic toxicity which, can be fatal.
- f). Temporary hyperpigmentation of the skin and nail bed changes.
- g). Grand mal seizures which can be prevented by the prophylactic administration of Dilantin.

3.2 VP-16 (VP-16-213) (Etoposide) (Vepesid)

3.21 Chemistry: VP-16 is a semi-synthetic podophyllotoxin derivative from the plant *podophyllum peltatum*, has anti-neoplastic properties in experimental animals and in man. The empiric formula $C_{29} H_{32} O_{13}$ has a molecular weight of 588.

3.22 Mechanism of Action: The epipodophyllotoxin exert phase-specific spindle poison activity with metaphase arrest, but in contrast to the vinca alkaloids, have an additional activity of inhibiting cells from entering mitosis. Suppression of tritiated thymidine, uridine, and leucine incorporation in human cells in tissue culture suggest effects against DNA, RNA and protein synthesis.

3.23 Animal Tumor Data: Significant anti-tumor effect has been demonstrated in L-1210, mouse sarcoma 37 and 180, Walker carcinosarcoma and Erlich ascites tumor. With the L 1210 system,

activity was schedule-dependent, having greater effect with a twice a week administration than with daily dosing or the administration of single large doses. The drug is active given intraperitoneally or orally in L 1210. No effect was demonstrated intracerebrally inoculated L 1210.

3.24 Animal Toxicology: The predominant toxicities of VP-16 in animal studies involve the hematopoietic system, with toxicity to the liver and GI tract occurring only at doses producing profound myelosuppression. Anemia, leukopenia, and lymphoid involution occur in mice, rats and monkeys. Acute toxicity investigations have been complicated by the toxicity of the solvent system. The LD-50 of the solvent plus drug approached that of the solvent alone. Immuno-suppressive effects occur with an inhibition of antibody production in mice and monkeys, and prevention of experimental allergic encephalomyelitis in rats (cell mediated immunity).

3.25 Human Toxicology: Reversible myelotoxicity has been uniformly observed to be the major toxicity of VP-16 and to represent the only clinically significant side effect. Following a single IV injection, peak myelotoxicity occurs at 7 to 9 days. Following daily IV injections for 5 to 7 days, myelotoxicity is maximal between 12 to 16 days from the initiation of therapy. Bone marrow suppression is mainly manifested as granulocytopenia with thrombocytopenia and anemia occurring to a lesser extent. Transient, modest nausea, usually without vomiting, is common. Occasional alopecia is reported. VP-16 does not produce stomatitis, phlebitis, neurotoxicity, hepato-toxicity or nephro-toxicity. Hypotension and anaphylaxis are occasional side effects. Hypotension can be managed by infusing the drug over at least a 30 minute period. Occasionally, fever may be a result of VP-16 administration.

3.26 Pharmaceutical Data: Formulation: 100 mg of VP-16 is supplied as 5 ml of solution in clear ampules for injection. Each ampule also contains anhydrous citric acid 10 mg, benzylalcohol 150 mg, polysorbate 80 purified 400 mg, polyethylene glycol and absolute alcohol. The contents of the ampule are non-aqueous and must be diluted with 20 to 50 volumes of sodium chloride injection USP. The time before precipitation depends on concentration.

Dilution Time

| | |
|-------|------------|
| 1:20 | 30 minutes |
| 1:50 | 3 hours |
| 1:100 | 6 hours |

3.27 Storage and stability: The drug is available as a box of 10 ampules that are stored at room temperature. Each ampule should be kept in the box to protect it from light. VP-16 is less stable in 5% Dextrose injection and precipitation is reported. VP-16 has a minimum infusion time of 30 minutes to reduce hypotension.

3.28 Supplier: VP-16 is commercially available.

3.3 Cyclosporine:

3.31 Mechanism of Action: Cyclosporine is an immunosuppressant used to prevent the rejection of transplanted kidneys, hearts and livers. It is also effective in treating bone marrow recipients with acute graft vs host disease. The drug inhibits T lymphocyte function with minimal activity against B cells.

3.32 Human Toxicology: Nephrotoxicity is the most frequent side effect of cyclosporine. Other frequently observed side effects include hypertension, hirsutism, tremors, paresthesias, hepato-toxicity, hypomagnesemia and hyperkalemia. Transient gastrointestinal symptoms have also occurred, to include anorexia, nausea and ileus. The drug has demonstrated a relative lack of myelotoxicity.

3.33 Pharmaceutical Data: Formulation: Cyclosporine is available for oral and intravenous administration. Cyclosporine is an olive oil solution supplied in 50 ml bottles containing 100 mg/ml. The intravenous solution is available as 5 ml ampules containing 50 mg/ml. Cyclosporine is also available as 25mg and 100mg capsules.

3.34 Storage and Stability: The oral solution of cyclosporine should be stored and dispensed in the original container at temperatures below 86°F and should be used within two months after opening bottle. Do not store in the refrigerator. The intravenous solution should be stored at temperatures below 86°F and protected from light.

3.35 Administration: The oral solution may be mixed with whole milk, chocolate milk or fruit juice to mask the taste and should be taken immediately after mixing. Cyclosporine should be administered intravenously over 2 to 6 hours. Longer infusion times are acceptable and sometimes better tolerated. The contents of the ampule should be diluted with 50-250 ml of 0.9% sodium chloride injection or 5% dextrose injection.

3.36 Supplier: This drug is commercially available.

3.4 Methotrexate

3.41 Chemistry: Methotrexate is a well known antimetabolite which has been intensively studied.

3.42 Biochemistry: As a folic acid analog, methotrexate is considered to act as an inhibitor of dihydrofolate reductase to which it tightly binds.

3.43 Human Pharmacology: Methotrexate is well absorbed in low doses from the gastrointestinal tract and is well absorbed when given intramuscularly. Large doses are completely absorbed when given

orally. About 40-50% of small doses and about 90% of large doses are excreted unchanged in the urine within eight hours. Toxicity is directly related to the duration of blood levels and thus, renal insufficiency can significantly increase toxicity. In man, there is insignificant metabolism of methotrexate.

3.44 Human Toxicity: Human toxicity includes myelosuppression, mucositis, nausea and abdominal discomfort, generalized malaise, rashes, photosensitization, decreased renal function, fetal death, hepatic toxicity and pulmonary toxicity (methotrexate lung).

3.45 Pharmaceutical Data: Formulation; 50mg vials containing 25mg/cc.

3.46 Storage: Room temperature.

3.47 Administration: In this study, administered intravenously.

3.48 Supplier: Methotrexate is commercially available for purchase by the third party.

4.0 STAGING CRITERIA:

4.1 Definition of Disease Stages of Chronic Myelogenous Leukemia

Chronic Phase

1. No significant symptoms which are not readily controlled by conventional doses of hydroxyurea or busulfan.
2. None of the features of accelerated phase or blastic phase. (Note: Granulocytic hyperplasia and the Philadelphia chromosome may be present in the bone marrow).

Accelerated Phase (any one or more of the following criteria)

1. WBC difficult to control with conventional use of busulfan/hydroxyurea in terms of doses required or shortening of intervals between courses.
2. Rapid doubling of WBC (\leq 5 days).
3. \geq 10% blasts in blood or marrow.
4. \geq 20% blasts plus promyelocytes in blood or marrow.
5. \geq 20% basophils plus eosinophils in blood.
6. Anemia or thrombocytopenia unresponsive to busulfan/hydroxyurea.
7. Persistent thrombocytosis (\geq 1,000,000/ 1) unresponsive to conventional doses of hydroxyurea or busulfan.

8. Additional chromosome changes (evolving new clone).
9. Increasing splenomegaly unresponsive to conventional doses of hydroxyurea or busulfan.
10. Development of chloromas or myelofibrosis.
11. Patients in a second (or subsequent) chronic phase after blast crisis.

Blastic Phase

1. $\geq 30\%$ blasts plus promyelocytes in the blood or bone marrow.

5.0 ELIGIBILITY CRITERIA

5.1 Inclusion Criteria

- 5.1.1 Patients with acute myelogenous or lymphocytic leukemia who are not in first remission or second remission i.e. after failing remission induction therapy or in relapse or beyond second remission, or patients with chronic myelogenous leukemia in blastic phase of the disease are eligible for the study. Patients with refractory anemia with excess blasts and in transformation will be eligible.
- 5.1.2 All candidates for this study must have a HLA (A,B,C,DR) identical siblings who is willing to donate bone marrow for marrow grafting. All ABO blood group combinations of the donor/recipient are acceptable since even major ABO compatibilities can be dealt with by various techniques. (Red cell exchange or plasma exchange). Peripheral blood stem cells or bone marrow can be used.
- 5.1.3 Prior therapy with VP-16 and busulfan is allowed.
- 5.1.4 Patients must be older than 16 and the upper age limit is physiological age of 50.
- 5.1.5 A cardiac evaluation with electrocardiogram and MUGA or echocardiogram is required in all patients. Patients must have an ejection fracture of greater than or equal to 50%.
- 5.1.6 Patients must have a serum creatinine of less than or equal to 1.2 or creatinine clearance $> 80\text{ml/min}$.
- 5.1.7 A bilirubin of less than or equal to 1.5. Patients should also have an SGOT and SGPT less than 5 times the upper limit of normal.
- 5.1.8 Pulmonary function tests including DLCO will be performed. FEV₁ and DLCO should be greater than 50% of predicted normal value.

5.1.9 The time from the last induction or reinduction attempt should be greater than or equal to 28 days.

5.1.10 Signed informed consent form approved by the IRB is required. The patient, family member and transplant staff physician (physician, nurse, and social worker) meet at least once prior to starting the transplant procedure. During this meeting all pertinent information with respect to risks and benefits to donor and recipient will be presented. Alternative treatment modalities will be discussed. The risks are explained in detail on the enclosed consent forms.

Revised 8/28/00

Revised 3/11/02

Revised 6/13/02

5.1.11 Patients with AML in first remission with poor risk cytogenetics (11q abnormalities, -7,-5, complex abnormalities i.e. > 3 abnormalities, 6;9 translocation and 3q abnormalities del (7q), del (5q), complex abn ≥ abnormalities, 9q, 20q, 21q, 17p, t(9;21)).

5.2 Exclusion Criteria

5.2.1 Prior radiation therapy that will exclude the use of total body irradiation.

5.2.2 Patients who have undergone bone marrow transplantation previously and who have relapsed.

5.2.3 Patients with psychological or medical condition that patients physician deems unacceptable to proceed to allogeneic bone marrow transplant.

Revised 8/28/00

5.2.4 Pregnancy

5.3 Donors

5.3.1 Any sibling donors who are histocompatible with the prospective recipient will be considered as a suitable donor.

5.3.2 Donors will be excluded if for psychological or medical reasons they are unable to tolerate the procedure.

5.3.3 Donor should be able to donate peripheral blood stem cells or bone marrow.

6.0 TREATMENT PLAN

All patients will have a right atrial catheter, hickman type inserted. This catheter will be used for collection of blood specimens, administration of drug, bone marrow, blood components, and for hyperalimentation.

Revised 8/28/00

6.1 Pre-transplant evaluation *will be performed within four weeks of beginning treatment except for the following: 1) Bone marrow aspirate and biopsy + cytogenetics within 14 days of starting treatment, 2). CBC, differential, platelets, comprehensive metabolic panel within 5 days of starting treatment.*

a). Prior to admission patient will have a complete history and physical examination performed. Special attention will be given to prior

chemotherapy, height, weight and body surface area should also be noted.

b). Patients will have the following laboratory tests performed:

- i. CBC with diff platelets
- ii. Sodium, potassium, chloride, bicarbonate or total carbone dioxide, BUN, creatinine, Ca, Mg, Phosphorous, total bilirubin, total protein, albumin, SGPT, SGOT, LDH, alkaline phosphatase, cholesterol, glucose.
- iii. Urine analysis
- HIV test
- Hepatitis A,B + C
- 24-hr urine for creatinine clearance
- CMV, HSV – HZV ab
- Immunoglobulin levels
- iv. 24-hour urine collection for creatinine clearance.
- v. Chest x-ray and EKG
- vi. CT scan chest, abdomen and pelvis.
- vii. Pregnancy test

Revised 8/28/00

- c). Initial coagulation studies prothrombin time, APTT.
- d). MUGA scan or echocardiogram
- e). Pulmonary function tests
- f). A bone marrow aspirate and biopsy, and cytogenetics needs to be done within 2 weeks of admission (if bone marrow not aspirable and > 20% blasts in blood this may be done on peripheral blood sample).
- g). Patients with acute leukemia or chronic myelogenous leukemia in blast crisis will have a lumbar puncture performed. Methotrexate (10mg/m² but not more than a total dose of 12mg) will be administered intrathecally. The spinal fluid will be examined for the presence of malignant cells. Those patients who had leukemic CNS involvement prior to the time of admission before transplantation will receive five weekly intrathecal methotrexate injections with the dose described above from the time patients platelet count is greater than 75,000 to day 100, then monthly intrathecal methotrexate injections with the dose described above between day 100 and 12 months after transplantation. The initial spinal tap will only be performed if patients platelet count can be kept above 75,000.

6.2 Preparative Chemotherapy Regimen

Rev. 8/12/02

* Patient to sign consent form before starting Dilantin.

Rev. 11/8/01

Friday/Day -18

Begin dilantin 300mg/p.o. t.i.d. times 1 day, then 300mg/p.o./IV daily times 14 days.

Tuesday/Day -14

Admission or outpatient, dilantin blood levels will be checked and dose adjusted as needed to meet therapeutic range. Further adjustments if clinically indicated. Busulfan test dose administered at 6 a.m. as a single dose. The I/V dose is calculated as follows:

1. Body surface area (BSA) is calculated by the equation:

$$\text{BSA} = \frac{(\text{Actual body wt.(kg)} \times \text{height (cm)})}{3600}$$

Rev. 6/13/02

2. 22mg/m² I/V Busulfan will be given over 2 hours. Blood levels will be obtained with the first dose as per appendix 1 and will be performed at City of Hope.

Rev. 11/8/01

Wednesday/Day -13

Busulfan AUC will be calculated by standard methods available in the City of Hope Analytical Pharmacology Core Facility (APCF). The resulting AUC will be used to determine the dose required to achieve an AUC of 800 $\mu\text{M}^* \text{min}$ according to the following formula:

$$\text{Adj dose} = \text{Current dose} \times \frac{800\mu\text{M}^* \text{ min}}{\text{test dose AUC}}$$

Rev. 6/13/02

The maximum dose given will not exceed 32mg/m². There is no limit on dose reduction Busulfan dose will only be adjusted for AUC's <700 or >900 $\mu\text{M}^* \text{min}$.

Thursday/Day -12

The adjusted dose Busulfan dose will be given at 6 a.m. and blood levels will be repeated. Further dose adjustments will be performed if AUC >1000.

Friday/Day -11

Patient admitted to BMT or receive further dose of Busulfan in clinic.

Busulfan dosing restarted at 6 p.m. and is repeated every 6 hours for a total of 14 doses.

Tuesday/Day -7

Fractionated TBI will be given at 120 cGy per fraction for a total of 4 days for a total of 10 fractions for a total dose of 1200 cGy. See Appendix II.

Saturday/Day -3

VP-16 30mg/kg based on adjusted ideal body weight will be administered.

Tuesday/Day 0

PSC reinfusion/or BM infusion

See Appendix 3 for PSC Collection

Toxicities of the marrow infusion are very rare. Volume overload may be prevented by removal of plasma from the marrow aspirate or by phlebotomy of the recipient prior to marrow infusion. Pulmonary emboli are theoretically possible and would require management with O₂ or IPPB. However, our clinical observations over the last 20 years indicate that pulmonary embolism in this clinical setting does

not occur at any increased rate. The most frequently encountered problem is that of chills, hives, and fever. Those allergic reactions occur rarely (in 1 to 2%) and can be prevented by intravenous injections of dyphenhydramine 25mg and hydrocortisone (50mg) prior to the bone marrow infusion.

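### As supplied, the section 6.2 body surface area equation has no square root; followed literally it inflates the busulfan test dose and the mg ceiling about 1.8-fold, while AUC targeting protects most of the course

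*Combined protocol and SAP*

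**What the plan says.** Section 6.2 (Day -14, item 1) states "Body surface area (BSA) is calculated by the equation". In the typesetting markup of the supplied text the equation reads "BSA} = \frac{(\text{Actual body wt.(kg)} \times \text{height (cm)})}{3600". That is a complete fraction with neither a radical nor a half-power.

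This BSA sets two quantities in section 6.2:

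- the single test dose on Day -14, at 22 mg/m²;
- the ceiling on Day -13: "The maximum dose given will not exceed" 32 mg/m².

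The test-dose AUC is then measured, and the dose is multiplied by 800 / test-dose AUC if that AUC is below 700 or above 900. Downward correction is unrestricted: "There is no limit on dose reduction". The Day -12 dose is measured again, with the rule "Further dose adjustments will be performed if AUC >1000". Fourteen more doses follow, so the course is 1 + 1 + 14 = 16 doses.

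No other BSA formula, worked BSA or mg dose appears in the document. Section 6.1a does ask that "chemotherapy, height, weight and body surface area should also be noted". The kinetics form in Appendix I records weights and the mg dose but has no BSA field.

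**The concern.** At 70 kg and 170 cm the supplied equation gives 3.31 m², which is not a credible adult BSA. The square root of the same fraction gives 1.82 m².

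The test dose is the exposed step. It is given before any drug level is known and cannot be taken back. Section 3.15 lists seizures and potentially fatal liver damage among busulfan's toxicities, and section 2.0 reports a narrow margin for the oral drug in this combination: "The dose limiting toxicity occurred at 12mg/kg the MTD was defined at 11mg/kg". The mg ceiling, the only absolute limit on the adjusted dose, rises by the same factor as the test dose.

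**Working it through.** **Inputs.** From section 6.2: the equation, 22 mg/m², 32 mg/m², the AUC target of 800, the no-adjustment band 700-900, and 16 doses. From section 2.0: oral MTD 11 mg/kg, DLT at 12 mg/kg, median first-dose AUC at the MTD 892 (range 460-1267). Assumed, because the document gives none: body sizes, and AUC proportional to dose. The plan states no BSA or mg dose, so there is no figure of its own to reproduce.

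**Step 1: BSA, test dose and ceiling.** Literal BSA = W × H / 3600; rooted BSA = √(W × H / 3600). The first is the square of the second, so literal / rooted = rooted BSA. At 70 kg and 170 cm: 70 × 170 / 3600 = 3.306, and its root is 1.818.

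| Assumed size | Literal BSA (m²) | Rooted BSA = factor | Test dose, literal / rooted (mg) | Ceiling, literal / rooted (mg) |
|---|---|---|---|---|
| 45 kg, 155 cm | 1.94 | 1.39 | 42.6 / 30.6 | 62.0 / 44.5 |
| 70 kg, 170 cm | 3.31 | 1.82 | 72.7 / 40.0 | 105.8 / 58.2 |
| 97 kg, 180 cm | 4.85 | 2.20 | 106.7 / 48.4 | 155.2 / 70.5 |

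At 70 kg and 170 cm the literal test dose is 72.7 / 1.818 = 40 mg per true m², against 22 intended.

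**Step 2: which form fits the protocol's own numbers.** Sixteen unadjusted doses at 70 kg total 16 × 40.0 / 70 = 9.1 mg/kg with the root and 16.6 mg/kg without it (16 × 72.7 / 70), against the oral MTD of 11 and DLT at 12. Scaling the phase I median AUC gives 892 × 9.14 / 11 = 741 with the root, inside 700-900, and 892 × 16.62 / 11 = 1348 without it. This treats the phase I doses as 16-dose totals and ignores oral bioavailability. It is rough, but it points to the rooted form as the intended one.

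**Step 3: the test dose.** If the intended dose would give 700-900, the literal dose at 70 kg and 170 cm gives 700 × 1.818 = 1273 to 900 × 1.818 = 1636. That is above the 1000 used on Day -12.

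**Step 4: the whole course, 70 kg and 170 cm.** Cumulative AUC = test-dose AUC + 15 × later AUC.

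| Intended test AUC | Literal test AUC | Later AUC, rooted / literal | Mean AUC per dose, literal | Cumulative, literal / rooted |
|---|---|---|---|---|
| 700 | 1273 | 700 / 800 | 13,273 / 16 = 830 | 13,273 / 11,200 = 1.19 |
| 800 | 1454 | 800 / 800 | 13,454 / 16 = 841 | 13,454 / 12,800 = 1.05 |
| 900 | 1636 | 900 / 800 | 13,636 / 16 = 852 | 13,636 / 14,400 = 0.95 |

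The ratio falls below 1 once the intended AUC exceeds about 846 (1.818a + 12,000 = 16a), because the rooted route then continues unadjusted above 800.

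**Step 5: the ceiling, 70 kg and 170 cm.** On the rooted route the ceiling binds when 22 × 800 / AUC > 32, that is when the test-dose AUC is below 550.

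| Intended test AUC | Later dose and AUC, rooted | Later dose and AUC, literal | Cumulative ratio |
|---|---|---|---|
| 350 | 58.2 mg, 509 | 91.4 mg, 800 | 1.58 |
| 400 | 58.2 mg, 582 | 72.7 mg, 727 | 1.27 |
| 450 | 58.2 mg, 655 | 72.7 mg, 818 | 1.27 |
| 500 | 58.2 mg, 727 | 64.0 mg, 800 | 1.13 |
| 550 | 58.2 mg, 800 | 58.2 mg, 800 | 1.04 |

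The larger ratios arise because the correct ceiling would have held most of these patients below target. The literal route's later AUC does not exceed 900.

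**The case against.** The strongest objection is that the page may be right. A radical is easily lost when a PDF is read by a program, and the supplied text shows other damaged symbols. In Appendix VII, for example, the grade 3 platelet-transfusion entry for BMT studies shows 23 transfusions in the main table and at least 3 in the BMT summary. The fit of the rooted form to the protocol's own numbers is also what one would see if the page were intact. This stands: the documents cannot settle whether the root is missing from the plan. The neighbouring dose-adjustment formula reads correctly, but that does not rule out a lost sign.

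Second, staff would probably notice 3.31 m². Section 6.1a gives them an occasion, and the item directly below the equation carries a 2002 revision mark. This lowers the chance of literal use, but it does not make the supplied rule correct.

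Third, the harm is limited. A reader might infer that the whole course is overdosed 1.8-fold. Section 6.2 does not support that: the AUC rule uses the mg actually given, so the BSA error drops out of later doses unless the ceiling or the no-adjustment band intervenes. A reader might also infer that the raised ceiling lets exposure overshoot. Under linear kinetics it does not. What is lost is the stated mg limit in patients with high clearance.

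Finally, setting the test-dose AUC against the phase I maximum of 1267 is weak evidence of harm. That figure comes from oral dosing in patients going on to a full course, not from one intravenous dose followed by correction.

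**Conclusion.** The point holds for the equation as supplied and is conditional on the source page. At an assumed 70 kg and 170 cm, literal use raises the single test dose from 40.0 to 72.7 mg and the ceiling from 58 to 106 mg. The factor is about 1.4 to 2.2 over the assumed adult sizes.

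For patients whose intended test dose would give 700-900, mean AUC per dose stays inside the target at about 830-852. Cumulative exposure ranges from about +19% to -5% against the rooted formula; +5% is the value at an intended AUC of 800 only. Below an intended AUC of 550 the mg ceiling no longer limits later doses as planned, but they stay within the target. These course figures assume dose-proportional AUC and that body size.

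The issue is therefore one high, irreversible test dose and a weakened mg limit. It is neither a proven error on the page nor an overdosed course.

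**What to change.** Check the equation on the source page of section 6.2. If the root is present, no change is needed.

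If it is absent, replace the equation by amendment with BSA (m²) = √[actual body weight (kg) × height (cm) / 3600], and add a worked example: 70 kg, 170 cm gives 1.82 m²; test dose at 22 mg/m² is 40 mg; ceiling at 32 mg/m² is 58 mg. Pharmacy should check its dose calculation against that example.

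The cost is one symbol, one line of text and a pharmacy check. Sample size and analysis are unaffected.
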